**7.2.2. Exclusion Criteria**

**7.2.2.1. Screening Exclusion Criteria**

Subjects with any of the following conditions (for ocular conditions, in the study eye) are not eligible to participate in the study:

- 1) Females who are pregnant, nursing or planning a pregnancy, females of childbearing potential who are not using a reliable method of contraception, or females who breast-feed or wish to breast-feed
- 2) Glaucoma criteria as follows:
  - Traumatic, uveitic, neovascular, or angle-closure glaucoma; or glaucoma associated with vascular disorders

## CLINICAL PROTOCOL

Date: September 16, 2016 Phase: Phase II Study Protocol No.: GC-009

1

## CLINICAL PROTOCOL

Date:	Phase:	Protocol No.:
September 16, 2016	Phase II Study	GC-009

8) Other ocular status as follows:

10) Subject status as follows:

- uncontrolled systemic disease (e.g., diabetes, hypertension) that could compromise their participation in the study

A 3D bar chart illustrating the distribution of 1000 samples across 10 bins. The x-axis represents the bin index (1 to 10), the y-axis represents the sample index (1 to 1000), and the z-axis represents the value (0 to 1). The distribution is highly skewed, with most samples in the first few bins and a long tail of low-value samples.

**CLINICAL PROTOCOL**

Date: September 16, 2016	Phase: Phase II Study	Protocol No.: GC-009
-----------------------------	--------------------------	-------------------------

In addition, the investigator or the Glaukos Medical Monitor may declare any subject ineligible for any sound medical reason.

**7.2.3. Criteria for Subject Exit Prior to Study Completion**  
Subjects exited after signing the informed consent form and prior to study completion will be handled according to the procedure stated in the protocol for enrolled, exited subjects as follows:

**7.2.3.1. Prior to Randomization**  
Subjects may be exited from the investigation if they fail to meet screening criteria, baseline criteria or randomization criteria as outlined in Sections 4.1, 4.2 and 6.2, if they withdraw consent, or if study randomization goals have been met.

**7.2.3.2. After Randomization**  
Subjects may be exited (discontinued) from the investigation in the event of a condition that may cause them harm if participation were to be continued. Subjects may also withdraw involuntarily.

**CLINICAL PROTOCOL**

Date: September 16, 2016	Phase: Phase II Study	Protocol No.: GC-009
-----------------------------	--------------------------	-------------------------

**7.2.3.2.1. Subjects Lost to Follow-up**

Subjects who do not return for their postoperative study visits and cannot be contacted within a reasonable timeframe via letter or telephone, will be considered lost to follow-up. The site will make at least three (3) telephone calls to the subject. If the three telephone contacts are unsuccessful, the site will send a registered letter with return receipt to the subject. The letter will request the subject to contact and return to the study site. If the subject does not contact the site within a week after the letter was received, he/she will be considered lost to follow-up. If the subject cannot be located or reached, the site will send a second registered letter (with return receipt) to the subject notifying them that they have been exited from the study due to lack of response on the part of the subject to the telephone calls and first registered letter. The site will then exit the subject from the study using the Study Exit CRF.

All attempts at contacting the subject (including telephone call logs, copies of registered letters and registered letter receipts) must be documented and maintained with the subject's study source documentation and CRFs.

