**CLINICAL PROTOCOL**

Date: September 16, 2016	Phase: Phase II Study	Protocol No.: GC-009
-----------------------------	--------------------------	-------------------------

These implants have the potential for providing important benefits to patients. The long duration of drug therapy provided by the implants (up to 3 years) avoids the problem of compliance with topical ocular hypotensive medications. In addition, the small clear corneal incision required for implantation and the minimally invasive implant size avoids some of the complications of more invasive surgical procedures for treating glaucoma.

Earlier versions of both models of the implant have been investigated in a clinical trial conducted in Armenia. The results from this trial have demonstrated the Model G2TR-[REDACTED] and G2TR-[REDACTED] implants to be potent IOP-lowering implants, with effectiveness being observed through up to 18 months. The implants were also generally well tolerated. Based on the overall efficacy and safety results from this initial international trial, the Model G2TR-[REDACTED] and Model G2TR-[REDACTED] implants are proposed for further clinical investigation in a U.S. and Philippines Phase II trial.

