7.3.5.13. Visit 15 (Month 24 Exam, 730 days ± 60)

[figure not shown]

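### The lost-to-follow-up rule can exit a subject while a late visit window is still open, with no later contact attempt and no stated route back

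*Protocol*

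**What the plan says.** The rule in Protocol 7.2.3.2.1 applies to "Subjects who do not return for their postoperative study visits and cannot be contacted within a reasonable timeframe via letter or telephone". The timeframe is not defined. The steps are:

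- Calls: "The site will make at least three (3) telephone calls to the subject."
- First letter: "If the three telephone contacts are unsuccessful, the site will send a registered letter with return receipt to the subject." It asks the subject to get in touch and come back.
- Waiting time: "If the subject does not contact the site within a week after the letter was received, he/she will be considered lost to follow-up." No waiting time is given for a letter that is never received.
- Second letter: a registered letter "notifying them that they have been exited from the study due to lack of response on the part of the subject". It is a notice and makes no further request for contact.
- Close-out: "The site will then exit the subject from the study using the Study Exit CRF."

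The section makes no distinction between arms, does not mention visit windows, and neither allows nor forbids return.

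Protocol 4.1 sets the windows. They widen from ±3 days at Day 10 and Weeks 4 and 6 to ±60 days at Months 24 to 36.

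On analysis, SAP 6.1.3 makes observed case the primary approach for continuous efficacy variables, and Protocol 9.6.5 imputes no missing safety values. SAP 7.1.10 schedules specular microscopy at Screening and Months 3, 12, 24 and 36.

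**The concern.** An exit converts one unanswered contact episode into missing data at every later visit. If the exit is filed while the missed visit could still be made on time, the site stops trying before the protocol's own deadline for that visit has passed.

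The data at stake are the long-term results that the SAP is written to report at the Month 36 lock. Each early exit thins the observed-case IOP summaries, lengthens the span over which LOCF carries a value, and adds non-responders under NRI. Endothelial cell density is the sparsest series: a subject exited between Months 12 and 24 loses both remaining measurements.

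The protocol's safeguards help little here. Section 7.3.5.17 asks for the Visit 19 safety assessments on the day of exit where possible, which is hardly feasible for someone who cannot be reached. Section 10 describes follow-up after exit only for adverse events still ongoing. By contrast, Section 10.7 keeps subjects who need further glaucoma surgery in scheduled follow-up to the end of the study.

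**Working it through.** The readable text gives no loss-to-follow-up rate, return rate or power calculation, so there is no plan figure to reproduce. The check is date arithmetic.

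**Inputs from the documents.** Target day and half-width *w* of each window (Protocol 4.1); a 7-day wait after receipt of the letter (Protocol 7.2.3.2.1).

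**Assumed inputs.** The days over which the calls are made and the delivery time of the letter are not given. Time from first call to lost status, *e* = calls + delivery + 7:

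- fast: 0 + 1 + 7 = 8 days
- middle: 7 + 5 + 7 = 19 days
- slow: 14 + 10 + 7 = 31 days

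**Contact starts on the target day.** Days left in the window at exit = *w* − *e*. A negative value means the window has already closed.

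| Visits | *w* | *e* = 8 | *e* = 19 | *e* = 31 |
|---|---|---|---|---|
| Day 10, Weeks 4 and 6 | 3 | −5 | −16 | −28 |
| Week 12 | 7 | −1 | −12 | −24 |
| Months 6, 9, 12 | 14 | 6 | −5 | −17 |
| Months 15, 18, 21 | 30 | 22 | 11 | −1 |
| Months 24 to 36 | 60 | 52 | 41 | 29 |

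**Contact starts on the first day of the window.** Days left = 2*w* − *e*. For *w* = 3, 6 − 8 = −2, so exit still falls after closing. For Week 12, 14 − 8 = 6 days remain in the fast case only (14 − 19 = −5).

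**Contact starts when the window closes.** Exit cannot fall inside the missed visit's own window. From Month 24, however, the windows overlap: days 670–790, 760–880, 850–970, 940–1060 and 1035–1155. Some window is open on every day from 670 to 1155. A Month 24 visit pursued from day 790 leads to exit between 790 + 8 = 798 and 790 + 31 = 821, inside the Month 27 window.

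**Visits at stake.** Visits 4 to 19 are 16 postoperative visits. Visits remaining after Month 6 (Visit 9): 19 − 9 = 10. After Month 12 (Visit 11): 19 − 11 = 8. After Month 24 (Visit 15): 19 − 15 = 4. These are upper bounds, because they assume that the subject would have returned at once and attended every remaining visit.

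**Scale per subject.** About 150 subjects at 1:1:1 is about 50 per arm, so one subject is 1/50 = 2% of an arm.

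**The case against.** The strongest case on the other side is that the rule is more patient than it looks. At least three calls come before the letter, and the week runs from receipt, not from mailing. The trigger speaks of visits in the plural and of an undefined timeframe, so a site may wait until the window has closed. Exit inside an open window is allowed, not required. This stands. It shows that the outcome depends on site practice; it does not show that the text prevents early exit.

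Second, a subject who cannot be reached gives no data whether or not a form is filed, and no return rate is readable. This also stands. A reader might infer that the data are given up needlessly, but the documents cannot show how many such subjects would have come back.

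Third, much of the protocol is blacked out, including the text of compliance monitoring (7.3.2), most visit procedures, visit windows (9.4.2) and missing-data handling (9.4.3). A provision for return could sit there. A reader might infer that exit is permanent; the readable text is only silent on this.

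Fourth, observed case is not the whole plan. The SAP adds LOCF, NRI and further sensitivity analyses that are partly hidden. These deal with missing values after the fact and do not replace measurements that could have been taken.

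Finally, keeping subjects open costs effort. Someone missed at Month 6 would stay open for up to 1155 − 182 = 973 days and ten later visits. That cost is real, but it falls only on subjects who cannot be reached.

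**Conclusion.** The point holds for long-term follow-up. As written, the rule lets a site close out a subject in any arm while a visit at Months 24 to 36 could still be made on time, with 29 to 52 days left under every assumed timing. At Months 15 to 21 the same happens in the fast and middle cases (22 and 11 days left), and at Months 6 to 12 only in the fast case (6 days left). These figures rest on contact starting on the target day and on the assumed 8 to 31 days.

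Two broader readings are not supported. A reader might infer that the primary endpoint is exposed in the same way. With a target-day start, exit falls after the window has closed at Day 10, Week 6 and Week 12, although an exit after an early missed visit would still lose any later primary visits. A reader might also infer that the loss concerns implanted eyes alone, but the sham/timolol arm is under the same rule.

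This is a cheap improvement that should be made. It does not threaten the 12-week comparison, and the total loss cannot be estimated from the documents.

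**What to change.** Amend Protocol 7.2.3.2.1 so that:

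- an unreachable subject is recorded as having missed that visit and stays on study;
- no exit is filed before that visit's window closes;
- contact is tried again at each later scheduled visit (because the late windows overlap, waiting for one window to close is not enough by itself);
- a subject who reappears may resume study assessments;
- final lost-to-follow-up status, with the date of last contact, is assigned at the end of the Month 36 window (1095 + 60 = day 1155), unless consent is withdrawn earlier.

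The same amendment should define the contact timeframe and say what happens when the letter is not delivered.

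The SAP needs two small matching changes. Section 7.1.1 computes exposure from the study exit date, so it should say how the last-contact date is used when exit is assigned late. Returners may also have gaps in study drops, because Protocol 6.1 dispenses kits at scheduled visits. Those gaps should be flagged in the IOP analysis. Whether drops restart is a clinical matter for the sponsor.

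The cost is a short amendment, some extra calls per missing subject and later closure of some records.

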**7.2.4. Study Termination**

This study may be stopped by Glaukos at any time following appropriate notification.

**7.3. Procedures**

Study visits and assessments are listed below, are provided in a table in Appendix A, and are detailed in Appendix I.

**7.3.1. Duration of Study**

Following a required washout/waiting period, the treatment period will be 3 years in duration.

**7.3.2. Methods to Monitor Subject Compliance**

In order to obtain reliable efficacy and safety data, it is critical that each study subject complies with the dosing schedule specified in this protocol. The following precautions will be taken to assure subject compliance during the study:

[figure not shown]
- [REDACTED]  
| [REDACTED]  
| [REDACTED]  
[REDACTED]

**CLINICAL PROTOCOL**

Date: September 16, 2016	Phase: Phase II Study	Protocol No.: GC-009
-----------------------------	--------------------------	-------------------------

[figure not shown]
**7.3.3. Enrollment**

All subjects must give written informed consent before undergoing any study-related change in their treatment or any study related procedures.

**7.3.4. Screening Phase**

**7.3.4.1. Visit 1 (Screening)**

**CLINICAL PROTOCOL**

Date:	Phase:	Protocol No.:
[REDACTED]	[REDACTED]	[REDACTED]

**7.3.4.2. Visit 2 (Baseline)**

[figure not shown]
[REDACTED]

[REDACTED]

[figure not shown]
[REDACTED]

**CLINICAL PROTOCOL**

Date: September 16, 2016	Phase: Phase II Study	Protocol No.: GC-009
-----------------------------	--------------------------	-------------------------

**7.3.5. Treatment Phase**

**CLINICAL PROTOCOL**

[figure not shown]
Date: September 16, 2016	Phase: Phase II Study	Protocol No.: GC-009
-----------------------------	--------------------------	-------------------------

**7.3.5.2. Visit 4 (Day 1-2 Exam 1-2 days)**

[figure not shown]
**CLINICAL PROTOCOL**

Date: September 16, 2016	Phase: Phase II Study	Protocol No.: GC-009
-----------------------------	--------------------------	-------------------------

7.3.5.3. Visit 5 (Week 1-2 Exam, 10 days  $\pm$  3)

[figure not shown]

7.3.5.4. Visit 6 (Week 4 Exam, 28 days  $\pm$  3)

[figure not shown]

**CLINICAL PROTOCOL**

Date: September 16, 2016	Phase: Phase II Study	Protocol No.: GC-009
-----------------------------	--------------------------	-------------------------

**7.3.5.5. Visit 7 (Week 6 Exam, 42 days ± 3)**

[figure not shown]
**CLINICAL PROTOCOL**

Date: September 16, 2016	Phase: Phase II Study	Protocol No.: GC-009
-----------------------------	--------------------------	-------------------------

**CLINICAL PROTOCOL**

Date: September 16, 2016	Phase: Phase II Study	Protocol No.: GC-009
-----------------------------	--------------------------	-------------------------

7.3.5.7      Visit 9 (Month 6 Exam, 182 days ± 14)

[figure not shown]

7.3.5.8.      Visit 10 (Month 9 Exam, 274 days ± 14)

[figure not shown]
**CLINICAL PROTOCOL**

Date: September 16, 2016	Phase: Phase II Study	Protocol No.: GC-009
-----------------------------	--------------------------	-------------------------

[figure not shown]

**CLINICAL PROTOCOL**

Date: September 16, 2016	Phase: Phase II Study	Protocol No.: GC-009
-----------------------------	--------------------------	-------------------------

7.3.5.10. Visit 12 (Month 15 Exam, 455 days  $\pm$  30)

[figure not shown]
**CLINICAL PROTOCOL**

Date: September 16, 2016	Phase: Phase II Study	Protocol No.: GC-009
-----------------------------	--------------------------	-------------------------

[figure not shown]
7.3.5.11. Visit 13 (Month 18 Exam, 547 days ± 30)

**CLINICAL PROTOCOL**

Date: September 16, 2016	Phase: Phase II Study	Protocol No.: GC-009
-----------------------------	--------------------------	-------------------------

[figure not shown]
7.3.5.12 Visit 14 (Month 21 Exam 637 days ± 30)

**CLINICAL PROTOCOL**

Date: September 16, 2016	Phase: Phase II Study	Protocol No.: GC-009
-----------------------------	--------------------------	-------------------------

7.3.5.13. Visit 15 (Month 24 Exam, 730 days ± 60)

[figure not shown]

7.3.5.14. Visit 16 (Month 27 Exam, 820 days ± 60)

[figure not shown]

**CLINICAL PROTOCOL**

Date: September 16, 2016	Phase: Phase II Study	Protocol No.: GC-009
-----------------------------	--------------------------	-------------------------

[figure not shown]

7.3.5.15. Visit 17 (Month 30 Exam, 910 days ± 60)

[figure not shown]

**CLINICAL PROTOCOL**

Date: September 16, 2016	Phase: Phase II Study	Protocol No.: GC-009
-----------------------------	--------------------------	-------------------------

[figure not shown]
7.3.5.16. Visit 18 (Month 33 Exam, 1000 days  $\pm$  60)

7.3.5.17. Visit 19 (Month 36 Exam, 1095 days  $\pm$  60)

**CLINICAL PROTOCOL**

Date: September 16, 2016	Phase: Phase II Study	Protocol No.: GC-009
-----------------------------	--------------------------	-------------------------

If a subject exits from the study before completing Visit 19, then to the extent possible, all follow-up safety assessments that are to be performed at Visit 19 should be performed on the day of exit.

**7.4. Concomitant Therapies**

**7.4.1. Prohibited Medications or Treatments**

[REDACTED]

**7.4.2. Permitted Medications or Treatments**

Therapy considered necessary for the subject's welfare that will not interfere with the evaluation of the study medication may be given at the discretion of the investigator.

**CLINICAL PROTOCOL**

Date: September 16, 2016	Phase: Phase II Study	Protocol No.: GC-009
-----------------------------	--------------------------	-------------------------

**7.4.3. Use of Contact Lenses**

Contact lens wear is allowed in this study. Subjects are to be instructed to remove their contact lenses in the study eye prior to instillation of study medications, and to wait for 20 minutes before inserting their contact lenses after instillation of study medication.

**7.5. Post-Treatment Management of IOP**

**7.5.1. Management of Postoperative Intraocular Pressure**

**7.5.2. IOP Increase to**

Subjects implanted with Travoprost Intraocular Implants

Subjects in the Topical Timolol Group

**7.5.3. IOP Increase to  $\geq$**

**CLINICAL PROTOCOL**

Date: September 16, 2016	Phase: Phase II Study	Protocol No.: GC-009
-----------------------------	--------------------------	-------------------------

7.5.4. IOP of [REDACTED]

or Later [REDACTED]

**8. EXTENT OF EXPOSURE AND TREATMENT COMPLIANCE**

Following the surgical procedure, all subjects will instill study medication (eyedrops) twice a day for 3 years. For those subjects assigned to the implant and placebo medication groups, the study medication will be artificial tears. For those subjects assigned to the sham surgical procedure and timolol group, the study medication will be topical timolol.

To ensure compliance with the treatment regimen, [REDACTED]

**9. STATISTICAL SECTION**

Statistical Methodology

9.1. Power Calculation and Determination of Sample Size

9.2. Statistical Hypotheses and Level of Significance

9.3. Unmasking of Randomization

**CLINICAL PROTOCOL**

Date: September 16, 2016	Phase: Phase II Study	Protocol No.: GC-009
-----------------------------	--------------------------	-------------------------

[REDACTED] For the

final analyses, when all subjects have completed the 12-week Visit, the randomization code will be unmasked to the project team after all the data queries related to the efficacy and safety outcomes have been resolved and corresponding data revisions have been completed in the database.

#### 9.4. General Principles of Data Handling

##### 9.4.1. Data Quality Review

Data screening will be conducted in a masked fashion periodically during the conduct of the study. The objective of the data screening is to assess the quantity, quality, and statistical characteristics of the data relative to the requirements of the planned analyses. Any questionable values or situations will be reported to the Medical Monitor for review and confirmation.

##### 9.4.2. Visit Windows

##### 9.4.3. Handling of Missing and Incomplete Data

**CLINICAL PROTOCOL**

Date: September 16, 2016	Phase: Phase II Study	Protocol No.: GC-009
-----------------------------	--------------------------	-------------------------

**9.5. General Statistical Considerations**

**9.5.1. Primary Efficacy Endpoint**

The primary efficacy endpoint is the IOP at 1 week through 12 weeks post-treatment. The difference in the mean IOP between the control group and each of the two

**9.5.2. Safety Outcomes**

The safety outcomes include surgical complications, adverse events, BCVA, slit-lamp biomicroscopy findings, change in gonioscopy findings, ophthalmoscopy findings (including cup/disc ratio), pachymetry, visual field evaluation, endothelial cell parameters, change from baseline in conjunctival hyperemia, periorbital measurements, iris color and eyelash density and length, and blood plasma testing to assess systemic exposure to the implant study medication (travoprost free acid).

**9.5.3. Planned Covariates**

The mean IOP comparison will be analyzed adjusting for each of the following covariates separately and all covariates simultaneously.

- 

**9.5.4. Analysis Populations**

**9.5.4.1. Intent to Treat Population (ITT)**

This subset includes all subjects who are randomized. All baseline characteristics will be summarized based on ITT. Subjects in the ITT will be analyzed according to original treatment assignment, regardless of actual treatment received. The primary analyses of the mean IOP comparisons will be based on this ITT population.

**9.5.4.2. Safety Population**

**CLINICAL PROTOCOL**

Date: September 16, 2016	Phase: Phase II Study	Protocol No.: GC-009
-----------------------------	--------------------------	-------------------------

The safety analysis population will contain all subjects who are randomized, receive treatment, and at least one study medication drop. Subjects will be grouped according to their actual treatment received, not according to their randomization assignment (as randomized). If subjects receive the incorrect medication eyedrops, they will be grouped according to the actual treatment they received, not the medication eyedrops they had been assigned.

**9.5.4.3. Per Protocol Population (PP)**

The Per Protocol Population is a subset of ITT. It includes all the ITT subjects who received the treatment and medication drops based on the randomization schedule and do not have the major protocol deviations. The major protocol deviations will be determined with the study Medical Monitor in a mask fashion prior to the database lock for the final analyses for the 12-week data. The PP population will be used in the sensitivity analysis for the mean IOP comparisons.

